Weight loss intervention. The 6-month intervention will include dietary and exercise counseling and tips to help participants meet their healthy lifestyle goals. Participants will receive personalized calorie and physical activity goals to help them achieve a healthy weight loss of 1-2 pounds per week. Breastfeeding women will receive daily calorie goals that will facilitate weight loss while accounting for energy needs to support lactation; weight loss expectations do not differ by breastfeeding status. Participants will be encouraged to increase physical activity to 150 minutes per week of moderate intensity activity. While we will provide information about specific exercises designed to help with recovery from childbirth (e.g., pelvic floor exercises), participants will not be required to engage in any particular exercises or activity program. Counselors will encourage and support participants to make a plan for incorporating regular physical activity into their lives in a way (i.e., duration per session, frequency per week) that works for that individual woman. We will encourage participants to track their diet and exercise daily. We will encourage participants to use My Fitness Pal to track their diet and activity. In the in-person condition, the intervention will be delivered via weekly 90-minute group meetings for the first four months and then every other week in months 5 and 6. In the Facebook condition, the intervention will be delivered via a secret (private) Facebook group. See section 3.D.2.2.9 (3.D.2.2.9.1 through 3.2.2.9.6; pages 9-10) of the enclosed grant application for more details on the interventions.

Due to weather or to prevent spread of illness (e.g., coronavirus), we may hold intervention meetings for the in-person condition via video or telephone conference call.

Weekly time survey. Weekly, participants in both treatment conditions will complete a brief online survey to report current weight and time spent on Facebook. We expect the survey to take less than 5 minutes. The survey will be administered via REDCap. A copy of the weekly survey is enclosed.

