Participants will be screened for ability to engage in physical activity. Medical conditions preventing the increase of physical activity will be exclusionary. We will obtain medical clearance from each participant's primary care provider (PCP) or obstetrician/gynecologist (OB/GYN) including clearance to participate in physical activity. Participants who experience discomfort will be asked to meet with their PCP /OBGYN prior to returning to physical activity.

At the beginning of each study assessment, participants will be reminded that they do not have to answer any question they do not wish to, either in the focus group or surveys, and that they are free to leave at any time. The focus group leader will ask participants not to share information they learned about other participants during the group with others outside of the focus group. We will audio record the focus group discussion. We will ask participants to say their first name before she offers an opinion or answers a question. When we transcribe the audio recordings, we will remove participants' name and enter study ID instead. All participant surveys will be completed via a secure web form via REDCap. Additional efforts to protect participant confidentiality are described below.

For participants randomly assigned to the Facebook condition, information posted on Facebook is subject to Facebook's terms of use and privacy policy, including terms of use for their website and mobile application. As all eligible participants already use Facebook, we will instruct participants to re-review these terms and the privacy policy. The Facebook group will be private ("secret") and posts are only available to group members. We will ask participants not to post their locations or contact information when talking to other study participants. We will also ask participants not to disclose that they are in a research study to protect confidentiality of other participants and not to share posts of the Facebook group with people not in the group. Online social interactions will be monitored by study staff to help ensure the protection of privacy. Intervention counselors will log into Facebook daily to deliver the intervention, engage with participants, and monitor online social interactions.

We suggest My Fitness Pal as a tool to help participants track their dietary intake and physical activity. We will ask participants who have an Android phone to download a free, commercially available app and

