2. who will conduct the monitoring (Under UConn policy a student cannot be the sole person responsible for monitoring the data and safety of the protocol procedures)
3. what data will be monitored (include compliance with approved IRB protocol)
4. how the data will be evaluated for problems
5. what actions will be taken upon the occurrence of specific events or end points
6. who will communicate to the IRB and how communication will occur
7. describe procedures to inform the sponsor

Sample response to issues listed above for minimal risk/ slight increase over minimal risk – “Survey results will be monitored by the PI in conjunction with the student investigator once every two weeks (items 1, 2 and 3). Survey responses will be reviewed to monitor for clarity (i.e., the same question is skipped by 5 or more participants). In that case, the question will be revised and an amendment will be submitted to the IRB (items 4, 5 and 6).”

Every two weeks (item 1), the PI and research coordinator (item 2) will review survey responses and collection and storage of additional data (item 3) to insure compliance with study protocols (item 4). Any deviations to protocol or adverse event reported by participants will be reported to the IRB through the appropriate process via InfoEd (item 5) by the PI (item 6), and we will submit an amendment if appropriate (item 5). The report of adverse events is built into our tracking database. Staff will assess the presence of adverse events during all participant contacts. We will report to NIH any serious unanticipated harms or unexpected threat to privacy as appropriate (item 7). We will convene a Data Safety and Monitoring Board (DSMB) to monitor the safety of participants throughout the proposed research, in particular for the occurrence of adverse events (both serious and otherwise). See attached grant proposal section 6 (pages 30-31).

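### Adverse events are assessed at participant contacts, but contacts differ by arm during treatment and no common adverse-event question on a common schedule is described

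*Protocol*

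**What the plan says.** The collection rule is in the protocol's Data Safety Monitoring section: "Staff will assess the presence of adverse events during all participant contacts". The text supplied does not define a contact and gives no standard question, recall period or timetable. The same section says that adverse-event recording is part of the tracking database, that the principal investigator and coordinator review survey responses every two weeks, and that a safety board will watch serious and non-serious events.

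Contact during treatment is set out under Design, Procedures, Materials and Methods. The in-person arm has "weekly 90-minute group meetings for the first four months and then every other week in months 5 and 6". If weather or illness intervenes, "we may hold intervention meetings for the in-person condition via video or telephone conference call", so those sessions stay live. For the other arm: "In the Facebook condition, the intervention will be delivered via a secret (private) Facebook group". The section on potential harms adds: "Intervention counselors will log into Facebook daily to deliver the intervention, engage with participants, and monitor online social interactions".

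One instrument runs weekly in both arms: "participants in both treatment conditions will complete a brief online survey to report current weight and time spent on Facebook". The protocol's list of measures for the baseline, 6-month and 12-month surveys includes a question on new pregnancies at follow-up but names no injury or adverse-event item.

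Exercise injury is the first risk the protocol names, and it states a response: "Participants who experience discomfort will be asked to meet with their PCP /OBGYN prior to returning to physical activity". The SAP covers feasibility and descriptive weight change and does not mention adverse events.

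**The concern.** A rule that assesses events at contacts is even-handed only if contacts are alike across arms. Here mode of contact is the randomized factor, so the opportunity to be asked about an event changes with the assignment.

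Two things are at stake. The first is protection of participants. The stated response to discomfort works only if staff hear of it. The protocol itself expects silent Facebook participants: its data analysis plan includes a secondary participation measure that counts reported lurking, and its background notes that some posts in the one-arm pilot drew little or no response. For a woman who reads without posting, the text describes no occasion during treatment when staff would ask her.

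The second is how the counts are read. The safety board will see events from two arms gathered by two different processes, and the investigators will use the pilot to plan a larger non-inferiority trial. Non-serious events depend most on being asked about. A difference in recorded counts could reflect who was asked and how, rather than what happened.

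**Working it through.** The plan states no number of sessions, contacts or expected adverse events, so it has no figure of its own on this point to reproduce. The check counts scheduled contacts and then shows how far unequal capture could move recorded counts.

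**Step 1. Scheduled contacts per woman during treatment**

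In-person sessions = weekly sessions in months 1–4 + fortnightly sessions in months 5–6.

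- Four-week months: 4 × 4 + (2 × 4)/2 = 16 + 4 = 20.
- Calendar months (365.25/12/7 = 4.35 weeks): 4 × 4.35 + (2 × 4.35)/2 = 17.4 + 4.3 = 21.7, about 22.
- With attendance of 50% to 100% (assumed), sessions actually attended run from 0.5 × 20 = 10 to 22.

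Weekly surveys = 6 × 4.35 = about 26, if they run throughout treatment.

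| Contact during treatment | In-person | Facebook | Adverse-event question described? |
|---|---|---|---|
| Scheduled live sessions | 20–22 | none described | only through the general rule |
| Counselor activity in the private group | none | daily, asynchronous | only through the general rule |
| Weekly online survey | about 26 | about 26 | none; weight and Facebook time are named |

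The 6- and 12-month assessments are common to both arms. The general rule applies to staff contact there too, but the 6-month assessment comes at the end of treatment.

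**Step 2. Effect of unequal capture on recorded counts**

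Expected recorded events = n × true event rate × probability that an event is captured. From the Justification of Sample Size, n = 36 per condition. The documents give neither a rate nor a capture probability. Assume the same true rate of 0.3 events per woman in both arms, so 36 × 0.3 = 10.8 true events per arm.

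| Assumed capture, in-person / Facebook | Recorded, in-person | Recorded, Facebook | Ratio |
|---|---|---|---|
| 0.9 / 0.9 | 10.8 × 0.9 = 9.7 | 10.8 × 0.9 = 9.7 | 1.0 |
| 0.9 / 0.6 | 9.7 | 10.8 × 0.6 = 6.5 | 1.5 |
| 0.9 / 0.3 | 9.7 | 10.8 × 0.3 = 3.2 | 3.0 |
| 0.6 / 0.9 | 6.5 | 9.7 | 0.67 |

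The ratio is simply the ratio of the capture probabilities; the assumed event rate cancels. The table shows that the distortion can run either way. It does not estimate its size.

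**The case against.** The rule covers all contacts, not only live ones. Counselors are in the Facebook group every day, and a written post may reveal an injury as readily as a 90-minute group meeting, where nothing says each woman is asked individually. In-person women can stop attending, just as Facebook women can stop posting. Both arms have staff contact at 6 and 12 months, when events missed earlier can still be reported. The SAP plans no comparison of events by arm, the protocol rates the study at or slightly above minimal risk, and events are routed to the ethics board, the funder and the safety board to protect participants. The survey forms and the grant's safety section are cited but were not supplied, and may contain an adverse-event question.

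Most of this stands, and it limits the claim. A reader might infer that Facebook women have no contact at which events could be found; daily counselor activity and the weekly surveys contradict that. A reader might also infer that the Facebook arm is bound to look safer; neither direction nor size can be derived.

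What the objection does not remove is the difference in process. Monitoring posts is not the same as asking each woman. An event surfaces in the group only if she chooses to disclose it to the other members. The later common assessments can recover an event for the record, but too late for a timely response during treatment.

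**Conclusion.** The point holds as a risk of differential ascertainment, not as a demonstrated bias. In the supplied text, assessment of adverse events follows contacts whose type and frequency differ by arm: about 20 to 22 scheduled live sessions against asynchronous group contact. The one weekly instrument common to both arms is not described as asking about events. Recorded counts may differ for that reason alone, by an amount and in a direction the documents leave open. For a Facebook woman who does not post, the delay before staff learn of an event could be as long as the six-month treatment period.

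This rests on the protocol's short descriptions of the surveys and on there being no live Facebook session in the intervention details held in the grant application. If the enclosed forms already carry a common question, the remaining step is to say so in the protocol.

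It would go too far to conclude that a false safety advantage for Facebook will pass into the later trial. No by-arm safety inference is planned, and that trial's stated hypotheses concern weight loss and cost-effectiveness. Nothing in the SAP's feasibility or weight reporting is affected. The case for acting is better protection during treatment and counts the safety board can interpret, at very little cost.

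**What to change.** Unless the enclosed forms already do this, add one standard adverse-event item to the weekly REDCap survey in both arms, with a fixed recall period. For example: since your last survey, have you had any injury, new medical problem, or emergency or hospital care; if so, please describe it. Repeat it in the 6- and 12-month surveys with a matching recall period. Handle positive answers under the process already in the protocol.

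Base any by-arm counts given to the safety board on this common source, and show survey completion by arm beside them, since a skipped survey is also a missed question. List events learned only at sessions or on Facebook separately; they still need action and reporting. State in the Data Safety Monitoring section what counts as a contact.

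The cost is one item in a survey expected to take less than 5 minutes, a minor amendment, and more minor events to record and report.

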Study title: The Healthy Moms Study: Comparison of a Post-Partum Weight Loss Intervention
Delivered Via Facebook or In-Person Groups

NCT 03700736

Statistical Analysis Plan

Date of document: 10/20/2021

Statistical Analysis

We will use Research Electronic Data Capture (REDCap) to administer participant surveys and for participant tracking and data management. We will use SAS 9.4 (SAS Institute, Inc., Cary, NC) to analyze quantitative data. Reporting of the feasibility outcomes and exploratory outcome of weight change will be descriptive (e.g., percent retention at 6 and 12 months).

Primary Outcomes: Feasibility

Examination of feasibility outcomes will inform the design of the subsequent full-scale non-inferiority trial.

Recruitment. We will report recruitment using a CONSORT diagram. We will compare yield from different recruitment approaches, and will examine whether any eligibility criteria are excluding an inordinate proportion of otherwise eligible women. In particular, we will examine the number of otherwise-eligible women excluded from participation because one or the other delivery mode is not feasible or unwillingness to be randomized to either treatment condition. If recruitment rates are lower than expected, we will adjust recruitment timelines as we plan the subsequent non-inferiority trial.

Sustained participation. We will report sustained participation in both conditions. We will modify the delivery of both intervention conditions to address logistical and other barriers to sustained participation.

Contamination. We will report the extent of contamination and reasons women sought these extra sources of support. If a significant proportion of women report seeking weight loss support from other sources, we will adapt our intervention to better meet their needs to reduce the occurrence of contamination in the subsequent trial.

Retention. We will report retention in each condition. If retention is lower than expected, we will explore reasons for drop-out and make changes to the protocol to address these challenges. We will also report the proportion of participants who become pregnant within the study period.

Feasibility of assessment procedures. We will examine the extent and mechanisms of missing data, particularly measures of costs associated with delivering and receiving the intervention. For measures with an unacceptable amount of missingness, we will consider alternate measures in the subsequent non-inferiority trial. We will resolve any issues arising in the collection of data needed for the cost-effectiveness aim of the subsequent efficacy trial and develop procedures for assessing time spent on Facebook to participate in the intervention.

Weight loss (exploratory)

We will report percent weight loss at 6 months and 12 months in each treatment condition.
